9.5 Adverse Events and Serious Adverse Events

9.5.1 Classification of Adverse Events

Definition of an Adverse Event: "An **adverse event (AE)** is any untoward medical occurrence in a subject temporally associated with participation in the clinical study or with use of the experimental agent being studied. An adverse finding can include a sign, symptom, abnormal assessment (laboratory test value, vital signs, electrocardiogram finding, etc.), or any combination of these." All adverse events will be assigned a severity, attribution to the study, and a status (anticipated or unanticipated) as described below:

Classification of AE Severity: AEs will be labeled according to severity, which is based on their impact on the participant. An AE will be termed 'mild' if it does not have a major impact on the participant, 'moderate' if it causes the participant some minor inconvenience and 'serious' if it causes a substantial disruption of the participant's wellbeing.

AE Attribution Scale: AEs will be categorized according to the likelihood that they are related to the study intervention. Specifically, they will be labeled either definitely, probably, possibly, or unrelated to the study intervention based on the professional judgment of the site PI. Events categorized as probably or possibly related to study participation due to a drug effect or as a consequence of a study procedure will be considered related to study participation. An event is not considered related if it can be explained by a participant's underlying medical condition.

Unanticipated Status: AEs will be classified as anticipated or unanticipated. Unanticipated AEs are assessed by the PI and must be unexpected, related to study participation, and involve risk to the participants or others. Unexpected events are events that do not appear in the list of anticipated events given below. The AE attribution scale will be used to determine if events are related to participation in the study. Events are considered to involve risk to the participant or others if their safety, rights, or welfare are affected (even if the event did not result in harm).

List of Non-Serious Adverse Events:

- 1) Mild hypoglycemia not requiring medical attention
- 2) Side-effects of medications (e.g. hepatic dysfunction or myopathy due to statins; dry cough due to ACE-I; negative effects of drugs on biochemical parameters such as hypo- or hyper-kalemia, hyperuricemia; and others per Investigator discretion)
- 3) Peripheral vascular disease: intermittent claudication, rest pain

- 4) Allergic reactions/reactions on basis of drug interactions
- 5) Infection (skin infections, soft tissue infections)
- 6) Weight gain
- 7) Worsening of pre-existing conditions other than dyslipidemia, hyperglycemia and systemic hypertension
- 8) Clinically significant biochemical evaluations as per the PI's discretion
- 9) Mild to moderate retinopathy without diabetic macular edema
- 10) Common AEs from depression treatments include headache, dry mouth, insomnia, constipation, dizziness, fatigue, somnolence, diarrhea, and hyperhidrosis (excessive sweating); most are mild to moderate
- 11) Other AEs associated with depression treatment are flu-like symptoms, anxiety, sexual dysfunction, sleep disturbance, dizziness, appetite changes, and blurred vision

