7.1.1 Measures to Minimize Risk

Appropriate precautions will be taken to avoid harming the well-being of participants. Any potential adverse effects will be monitored and reported by the study investigators immediately to the relevant clinic research site ethics committees, the Madras Diabetes Research Foundation Institutional Ethics Committee (IEC), and Emory University Institutional Review Boards (IRB) for appropriate action.

Even though the potential for injury to research subjects due to the risks of the proposed procedures is judged to be minimal, all reasonable efforts will be made to minimize these risks through the exclusive use of properly trained and educated research personnel. Individuals who are injured by study procedures will be informed of their rights to and be offered treatment of the injury as part of the informed consent procedure and the prevailing local health policy. Specifically:

- Participants will be informed of their right to refuse to answer any survey question that makes them uncomfortable.
- Any undiagnosed disease or condition or abnormal test results that present during study testing will be brought to the attention of the Site Lead Investigator and the participant.
- The participant will be referred for emergency care for emergencies or to their personal physician or a community hospital or clinic (if he or she does not have a personal physician) for non-emergencies.
- Where mild injury / discomfort is caused to the participant, e.g. vasovagal attacks, needle-stick injury, etc., appropriate procedures will be followed to attend to this by study and medical staff
- The study will have trial insurance to cover any major injuries or discomfort encountered by participants if the harm is judged to be attributable to study procedures

Suicide/Self-Harm Risk:

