9.5.2 Serious Adverse Events

Definition of a Serious Adverse Event: "A **serious adverse event (SAE)** is any adverse event that results in one or more of the following outcomes: death; a life-threatening event; inpatient hospitalization or prolongation of existing hospitalization; a persistent or significant disability/incapacity; a congenital anomaly or birth defect; or an important medical event based upon appropriate medical judgment." SAEs are AEs in which the severity has been classified as serious. SAEs will be further assessed by the PI for study attribution and anticipated status using the criteria described above.

List of Serious Adverse Events:

- 1) Severe hypoglycemia requiring medical attention/hospitalization (a hypoglycemic episode associated with transient central nervous system dysfunction without other apparent cause in which the individual was unable to treat him/herself and had help from another person to administer glucose or glucagon)
- 2) Acute hyperglycemia (e.g., diabetic ketoacidosis [DKA])
- 3) CVD events: angina, non-fatal MI / unstable angina, revascularization procedure (angioplasty or CABG), TIA, stroke (non-fatal), arrhythmia
- 4) Gangrene or amputation due to diabetes-related peripheral neuropathy and peripheral vascular disease
- 5) Major bleeding (e.g., intracerebral or gastro-intestinal)
- 6) Renal: end-stage renal disease requiring renal replacement therapy (dialysis or transplantation)
- 7) Eyes: severe diabetes-related eye disease (defined as the requirement for retinal photocoagulation or similar treatment and development of diabetes-related blindness in either eye in a participant known not to have this condition at study entry)
- 8) Major infection: requiring hospitalization and/or parenteral antibiotics (UTI, skin infections, soft tissue infections, lower respiratory tract infections/physician-diagnosed pneumonia)
- 9) Inpatient hospitalization or prolongation of existing hospitalization
- 10) Suicidal ideation
- 11) Death
- 12) Any other major health conditions/events (important medical event based upon appropriate medical judgment)

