9.5.3 Reporting of AEs and SAEs

Information about the occurrence of any AEs or SAEs will be sought at all scheduled visits and any intermediate visits between CCs and intervention participants. AEs and SAEs will then be classified as anticipated or unanticipated.

Unanticipated SAEs will be reported promptly. Death (whether anticipated or unanticipated) will follow the same prompt reporting procedure. The Lead Site Investigator will ensure that there is adequate follow-up of each participant who has a serious adverse event. Also, the Lead Site Investigator should ensure that all regulatory requirements specified by the local, site-specific IRB are completed. The DSMB will regularly review all such events and provide recommendations to the Steering Committee of Investigators. Documentation of all such SAEs will be retained in the participant's trial folder for at least 3 years.

Prompt reporting of a death or unanticipated SAE requires the responsible Lead Site Investigator to report the event to the Coordinating Center within 24 hours of the Lead Site Investigator's knowledge of the event by completing a serious adverse event document by fax, email, or online submission and with notification by telephone. The clinic research site must report the death or unanticipated SAE to the local, site-specific ethics committee within 7 calendar days.

The Coordinating Center will report deaths or unanticipated SAEs to the DSMB, Emory IRB, and MDRF IEC within 7 calendar days, with appropriate follow-up reports and final resolution forms with supporting documents as per evolution of the disease. Unanticipated SAEs will be reported to NIMH within 10 business days. Deaths related to study participation will be reported to NIMH immediately (no later than 5 business days) from when the site PI learns of the event. Anticipated deaths will be reported to NIMH as part of the annual report. Death or unanticipated SAEs that occur within 15 days after the end of the scheduled follow-up visit will be reported in the same way as those that occur before the end of follow-up. In addition, any AE that occurs after the completion of the scheduled follow-up, and that the investigator deems due to the study intervention, will be reported in the same way.

Anticipated SAEs or those unrelated to the study intervention will be reported to the same individuals/entities on a monthly basis. Anticipated AEs and SAEs will be reported to NIMH in the annual progress report.

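### Section 9.5.1 ties 'unexpected' to a list it never identifies; read literally with the serious-event list, no non-fatal SAE during scheduled follow-up can trigger prompt reporting

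*Combined protocol and SAP*

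**What the plan says.** Section 9.5.1 sets three conditions, all required: "Unanticipated AEs are assessed by the PI and must be unexpected, related to study participation, and involve risk to the participants or others". It defines the first of them by exclusion: "Unexpected events are events that do not appear in the list of anticipated events given below".

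Two lists follow. The first, in 9.5.1, is headed "List of Non-Serious Adverse Events" and has 11 items. The second, in 9.5.2, is headed as the list of serious adverse events and has 12. Neither is labelled as anticipated. In the serious list, item 9 repeats part of the SAE definition, "inpatient hospitalization or prolongation of existing hospitalization", and item 12 reads "Any other major health conditions/events (important medical event based upon appropriate medical judgment". Section 9.5.2 asks the PI to judge each SAE's attribution and anticipated status by the criteria set out above it.

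On relatedness, the 9.5.1 attribution scale has four grades: definitely, probably, possibly and unrelated. Only probable and possible events are then counted as related. There is also an exclusion, beginning "An event is not considered related if it can be explained by a" and ending with the participant's underlying condition.

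Section 9.5.3 gives prompt reporting to unanticipated SAEs and to every death. For the rest, "Anticipated SAEs or those unrelated to the study intervention will be reported to the same individuals/entities on a monthly basis", and NIMH learns of anticipated events in the annual progress report. Section 9.5.3 also applies the prompt procedure to any AE after scheduled follow-up that the investigator attributes to the intervention.

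Two other sections bear on this. Section 9.4, on unanticipated problems, also admits events of increased severity, duration or frequency. Section 7.1.1 says, without mentioning anticipated status: "Any potential adverse effects will be monitored and reported by the study investigators immediately".

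**The concern.** A definition by exclusion works only if the reader knows which list is meant and that list is closed. Here the list is not identified, and the serious list ends in an entry wide enough to take in any important medical event. If that list decides what is anticipated, meeting the definition of an SAE already makes an event anticipated, and the unanticipated-SAE trigger has nothing to act on short of death.

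What is at stake is the speed of independent oversight. Section 9.1 charges the DSMB with monitoring suicide attempts, psychiatric hospitalizations and new diagnoses that pose significant risk, among other events. A related, non-fatal event of such a kind could wait for a monthly report, and for the annual report in NIMH's case, through wording alone. The four sites would also have no common rule for sorting events. No efficacy estimate or test is affected.

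**Working it through.** No sample size or event count enters this point. The check is an enumeration.

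**Step 1: match the SAE definition to the serious list.** Section 9.5.2 gives six outcome criteria.

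- Death: item 11.
- Hospitalization or its prolongation: item 9.
- Important medical event: item 12, in the same terms.
- Life-threatening event, persistent disability, congenital anomaly: no general entry of their own, but each falls under item 12 as another major health event.

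All six are covered. Setting death aside leaves 6 − 1 = 5 non-fatal criteria. All five are covered, so 5 − 5 = 0 can yield an event that is absent from the list.

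**Step 2: derive the status of non-fatal SAEs under each reading the text allows.**

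- *Reading A: both lists together are the anticipated list, with the 9.5.1 criteria only.* 0 of 5 criteria can give an unexpected event. This is the most natural literal reading, because these are the only event lists below the definition.
- *Reading B: only the non-serious list, inside 9.5.1, is meant.* All 5 can give an unexpected event unless an open-ended non-serious entry captures it. Item 2 (medication side-effects) can be extended at the investigator's discretion, and item 7 takes in the worsening of most pre-existing conditions. The result of A largely reverses.
- *Reading C: the 9.4 wording also governs SAE status.* All 5 can qualify if the event is more severe, longer or more frequent than expected.

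**Step 3: compare the reporting routes in 9.5.3 for a related, non-fatal SAE during scheduled follow-up.**

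- If unanticipated: 24 hours from the site to the Coordinating Center; 7 calendar days to the local ethics committee; 7 calendar days from the Coordinating Center to the DSMB, the Emory IRB and the MDRF IEC; 10 business days to NIMH.
- If anticipated: monthly to the same recipients, and annually to NIMH.

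Reading A sends every such event down the second route. Readings B and C can send the same event down the first.

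**Step 4: identify what stays prompt under every reading.** Deaths do, whatever their status, and so does any AE after scheduled follow-up that is deemed due to the intervention. Reading A therefore gives an odd ordering: a related, non-serious event after follow-up is reported promptly, while a related, listed, non-fatal serious event during the intervention is reported monthly.

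**Step 5: check the relatedness rule against its own scale.** The scale has four grades. Two (probably, possibly) are counted as related and one is unrelated, which leaves 4 − 2 − 1 = 1 grade, 'definitely', unassigned. Section 9.4 uses the same two-grade wording.

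**The case against.** The strongest reply is that the authors did not mean the serious list to settle anticipated status. It is headed as a list of serious events and can be read as saying what counts as serious. Section 9.5.2 asks the PI to assess each SAE's anticipated status, which would be pointless if all were anticipated already. Section 9.5.3 speaks of deaths as either anticipated or not, although death is item 11. This is good evidence of intent. It does not supply the missing list, and it leaves a site with three readings and no way to choose between them.

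A reader might infer that no non-fatal SAE can ever qualify, or that the prompt route can fire only for deaths. The documents do not support either absolute. Readings B and C are open on the text, and 9.5.3 sends intervention-related AEs after follow-up down the same route.

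A reader might also infer that the catch-all entries are what keep a suicide attempt from prompt reporting. That example turns mainly on the underlying-condition exclusion. An attempt attributed to depression is classed as unrelated, and 9.5.3 sends unrelated events to monthly reporting whatever the list says. Reserving expedited reports for related events is a design choice and is not disputed here.

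Participant protection does not rest on this route. Section 9 refers serious events to study physicians and emergency care, 7.1.1 sets out a suicide protocol covering both arms, and 9.5.3 makes the Lead Site Investigator responsible for follow-up and local requirements. Monthly reports still reach the DSMB and ethics committees. All of this limits the consequence to slower independent oversight. The conflict between 7.1.1 and 9.5.3 is secondary: 7.1.1 is a general statement, and 7.1 points to Section 9 for detail.

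**Conclusion.** The defect holds in a conditional form. Section 9.5.1 does not identify its anticipated list. If the two lists that follow serve as that list, 0 of the 5 non-fatal SAE criteria can produce an unexpected event during scheduled follow-up, and the unanticipated-SAE trigger in 9.5.3 is empty for that period. A related, non-fatal SAE then moves from the 24-hour, 7-calendar-day and 10-business-day limits to monthly reports, and to the annual report for NIMH.

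This rests on two assumptions: that both lists count, and that item 12 is read as widely as it is worded. If either is dropped, or if the 9.4 wording is applied, some or all of these events can return to the prompt route. That dependence is itself a fault, since sites could classify the same event differently. Separately, and on any reading, the relatedness rule literally leaves out events graded as definitely related.

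**What to change.** Amend the wording as follows.

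- Name one closed list of anticipated events in 9.5.1. Keep it separate from the list of what counts as an SAE, and leave out the catch-all entries (any hospitalization; any other major condition or event).
- Carry the 9.4 wording on increased severity, duration or frequency into 9.5.1, so that a listed event can still be unanticipated.
- Add 'definitely' to the grades that count as related, in 9.5.1 and in the matching sentence of 9.4.
- Reconcile 7.1.1, 9.4 and 9.5.1 to 9.5.3, so that one rule sets the route and timing for each class of event.

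The cost is protocol wording and some more expedited reports; no new staff or procedures are needed. The change leaves the underlying-condition exclusion in place. Events classed as unrelated on that ground, such as a suicide attempt attributed to depression, would still be reported monthly.

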9.5.2 Serious Adverse Events

Definition of a Serious Adverse Event: "A **serious adverse event (SAE)** is any adverse event that results in one or more of the following outcomes: death; a life-threatening event; inpatient hospitalization or prolongation of existing hospitalization; a persistent or significant disability/incapacity; a congenital anomaly or birth defect; or an important medical event based upon appropriate medical judgment." SAEs are AEs in which the severity has been classified as serious. SAEs will be further assessed by the PI for study attribution and anticipated status using the criteria described above.

List of Serious Adverse Events:

- 1) Severe hypoglycemia requiring medical attention/hospitalization (a hypoglycemic episode associated with transient central nervous system dysfunction without other apparent cause in which the individual was unable to treat him/herself and had help from another person to administer glucose or glucagon)
- 2) Acute hyperglycemia (e.g., diabetic ketoacidosis [DKA])
- 3) CVD events: angina, non-fatal MI / unstable angina, revascularization procedure (angioplasty or CABG), TIA, stroke (non-fatal), arrhythmia
- 4) Gangrene or amputation due to diabetes-related peripheral neuropathy and peripheral vascular disease
- 5) Major bleeding (e.g., intracerebral or gastro-intestinal)
- 6) Renal: end-stage renal disease requiring renal replacement therapy (dialysis or transplantation)
- 7) Eyes: severe diabetes-related eye disease (defined as the requirement for retinal photocoagulation or similar treatment and development of diabetes-related blindness in either eye in a participant known not to have this condition at study entry)
- 8) Major infection: requiring hospitalization and/or parenteral antibiotics (UTI, skin infections, soft tissue infections, lower respiratory tract infections/physician-diagnosed pneumonia)
- 9) Inpatient hospitalization or prolongation of existing hospitalization
- 10) Suicidal ideation
- 11) Death
- 12) Any other major health conditions/events (important medical event based upon appropriate medical judgment)

9.5.3 Reporting of AEs and SAEs

Information about the occurrence of any AEs or SAEs will be sought at all scheduled visits and any intermediate visits between CCs and intervention participants. AEs and SAEs will then be classified as anticipated or unanticipated.

Unanticipated SAEs will be reported promptly. Death (whether anticipated or unanticipated) will follow the same prompt reporting procedure. The Lead Site Investigator will ensure that there is adequate follow-up of each participant who has a serious adverse event. Also, the Lead Site Investigator should ensure that all regulatory requirements specified by the local, site-specific IRB are completed. The DSMB will regularly review all such events and provide recommendations to the Steering Committee of Investigators. Documentation of all such SAEs will be retained in the participant's trial folder for at least 3 years.

Prompt reporting of a death or unanticipated SAE requires the responsible Lead Site Investigator to report the event to the Coordinating Center within 24 hours of the Lead Site Investigator's knowledge of the event by completing a serious adverse event document by fax, email, or online submission and with notification by telephone. The clinic research site must report the death or unanticipated SAE to the local, site-specific ethics committee within 7 calendar days.

The Coordinating Center will report deaths or unanticipated SAEs to the DSMB, Emory IRB, and MDRF IEC within 7 calendar days, with appropriate follow-up reports and final resolution forms with supporting documents as per evolution of the disease. Unanticipated SAEs will be reported to NIMH within 10 business days. Deaths related to study participation will be reported to NIMH immediately (no later than 5 business days) from when the site PI learns of the event. Anticipated deaths will be reported to NIMH as part of the annual report. Death or unanticipated SAEs that occur within 15 days after the end of the scheduled follow-up visit will be reported in the same way as those that occur before the end of follow-up. In addition, any AE that occurs after the completion of the scheduled follow-up, and that the investigator deems due to the study intervention, will be reported in the same way.

Anticipated SAEs or those unrelated to the study intervention will be reported to the same individuals/entities on a monthly basis. Anticipated AEs and SAEs will be reported to NIMH in the annual progress report.

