5.3 Program of Care for Control Arm Participants

Participants randomized to the control arm will receive the existing standard care and treatment for their diabetes that is provided routinely at each site and their care provider will be notified regarding their depressive symptoms. As mentioned in Section 6.2, the physicians treating the control arm will also be provided with trainings regarding identification and care for people with depression. The control participants will have no contact with CCs and will only be contacted at 6-monthly intervals for assessment by the blinded outcomes assessor.

6 Study Procedures and Measures

Participants in both arms will be invited for outcomes assessments (“study visits” at 0, 6, 12, 18, 24 and 36 month time-points) by a blinded outcomes assessor at each site to collect biochemical and participant-reported measures (Table 4). Biochemical measures (glucose, HbA1c, cholesterol subfractions) will be collected via blood draws while BP and anthropometric measures will be collected using an automated sphygmomanometer, weighing scale, tape measure, and clinic-based stadiometers. Participant-reported outcomes will be collected via questionnaires.

Although the PHQ-9 will be used to identify and efficiently monitor depressive symptoms and severity, regular use of the PHQ-9 leads to test-retest bias. As a result, we will use the Symptoms Checklist (SCL-20) depression scale as our main depression outcome measure.²³ This tool is very sensitive to changes in depression among people with diabetes and will be used for baseline, 6-monthly and 36 month measures only. It has also been used successfully in prior studies.² The PHQ-9 will still be administered at the 6-monthly study visits.

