6.1 Schedule of Evaluations

VISIT 1–PHQ-9 Screening; Eligibility Screening and Baseline Randomization; 6-monthly Visits for All

Table 4: Schedule of Evaluations

PHASE	Screening	Eligibility testing & baseline (0 month study visit)	Intermediate visits (Intervention Grp)	6-monthly study visits	Sustained effectiveness visits
MONTH	Max -4 weeks	-4 to 0 weeks		6, 12, 18	24 and 36 month visits
Verbal consent	X	X			
Signed informed consent		X			
PHQ-9	X	X	X	X	X
SCL-20		X		X	X
Assess Eligibility + Enrollment	X	X			
Demographics (age, sex, socioeconomic status)		X			
Medical history	X (basic)	X (full)	X (interval)	X (interval)	X (interval)
Family history		X			
Social History (lifestyle/habits)		X	As needed	X	X
Questions regarding Bipolar Disease / Psychosis		X		X	X
Anxiety (GAD-7)		X		X	X
Alcohol use (AUDIT-10) and drug use (DAST-10)		X			X
Cognitive function (MoCA)		X			X
Self-care (SDSCA)		X		X (partial)	X
Quality of Life(HUI-3)		X			X
Diabetes Treatment Satisfaction (DTSQ)		X			X
Costs of Care (records, questionnaire)		X			X
*Acceptability: physician interviews		Likely			Likely
Blood pressure (BP) and heart rate	X	X	As needed	X	X
Height, Weight, BMI (calculated), Waist Circumference		X	As needed	X	X
General Physical Examination		X	As needed	X	X
Eye Examination		X	As needed	As needed	X
Foot Examination		X	As needed	As needed	X
ECG		X	As needed	As needed	X
Urine Microalbuminuria		X			X
Albumin:creatinine ratio (urine analysis)		X			X
†Serum Creatinine Serum Sodium, Potassium and ALT		X	As needed		X
Venous fasting blood glucose (FBG)		X	As needed	X	X
Glycated hemoglobin A1c		X	As needed	X	X
Lipids (TC, HDL, LDL [calculated], TG)		X	As needed	X	X
Glucose-lowering, blood-pressure lowering, and cholesterol-lowering medications		X	As needed	X	X
Other concomitant medications		X	As needed	X	X
Tobacco use		X	As needed	X	X
AE/ SAE Intake (ongoing)			X	X	X

*Qualitative interviews of physician sub-samples will be administered by Coordinating Center staff.

†Follow-up serum potassium and creatinine levels if high and started on ACE-i; follow-up ALT if started on statin.

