Participants randomized to the usual care group will have no additional direct contact with the study staff. The routine care providers of usual care participants will be provided with written guidance on how to manage depressive symptoms and provide the most updated evidence-based guidelines for care of diabetes and CVD (e.g., American Diabetes Association guidelines). As such, the usual care providers may request usual care participants to visit the clinic more frequently or may intensify treatments. We will assess these changes at outcomes assessment visits.

Participants randomized to the intervention group will have additional visits and follow-up with the CC interventionist. These “interim” visits will involve an initial visit and at least 4 visits over the course of the 12-month active intervention. There may also be more visits and more phone contact, lasting from 10 minutes for brief progress checks to more detailed 60-minute visits to use behavioral activation or motivational interviewing techniques to encourage better self-care. Participants will not be compensated for these visits and phone calls. If additional tests or changes to treatment plans are required based on guidance from the DS-EHR, the usual care physician, or our case review team, the costs for these intermediary tests or treatment adjustments will be borne by participants as this is an implementation trial. As mentioned, all study-related outcome assessment visit costs (the six-monthly “study visits”) are borne by the study team.

Throughout the screening and study process, potential participants will be treated with respect and reassured that they have the right to withdraw from the screening process or the study at any time without any consequence for their usual care. All clinic interactions and activities will be conducted in a private room and the in the preferred language(s) of the local regions to assure participants’ comfort.

8 Study Benefits

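### Adverse events are asked about at care-coordinator contacts in the intervention arm only, so by-arm counts of events that depend on being asked would tend to be inflated in that arm

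*Combined protocol and SAP*

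**What the plan says.** Section 9.5.3 sets the elicitation rule: AE and SAE information "will be sought at all scheduled visits and any intermediate visits between CCs and intervention participants". The schedule of evaluations (Table 4, section 6.1) agrees. It marks AE/SAE intake, and also the PHQ-9, in the intermediate-visit column, which is headed as applying to the intervention group.

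For the other arm, section 5.3 says: "The control participants will have no contact with CCs and will only be contacted at 6-monthly intervals for assessment by the blinded outcomes assessor". Section 7.3 adds: "Participants randomized to the usual care group will have no additional direct contact with the study staff". The same section requires interim visits to be documented in the DS-EHR for intervention participants but not for controls.

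Section 7.3 gives the minimum number of coordinator visits as "an initial visit and at least 4 visits over the course of the 12-month active intervention". The example schedule in Table 2 is denser, with monthly contact in weeks 25 to 52.

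At the common visits (6, 12, 18, 24 and 36 months) the blinded assessor takes an interval history, including AEs and SAEs, from both arms (section 6.2.2).

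The SAE list in section 9.5.2 includes "Suicidal ideation". Section 9.1 makes ideation one of the events the DSMB monitors, and section 9.3 requires an annual AE summary that compares rates with what was expected before the study. Section 10 contains no safety analysis. No section asks for the source of an event to be recorded or says how events from the two kinds of contact should be tabulated.

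**The concern.** If two arms have the same true event rate and one is asked more often, more events are recorded in the arm asked more often. Here the difference is written into the collection rule, and it runs with treatment assignment.

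The detection also differs in kind. Coordinators know the participant's arm, whereas the assessor at the common visits is blinded. PHQ-9 item 9 looks back only two weeks, so ideation that comes and goes between 6-monthly control visits can be missed by that item, while coordinator contacts sample many more two-week windows in the intervention arm.

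The DSMB reviews these events and makes recommendations, and section 9 allows for early discontinuation of the trial. A by-arm count prepared for the DSMB, or published later, could suggest harm that is partly or wholly a product of more frequent questioning. The efficacy outcomes are not affected.

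**Working it through.** The plan states no safety figure that could be reproduced, so the check counts elicitation points and then illustrates what unequal counts do when true rates are equal.

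**Step 1. Elicitation points in year 1**
- Both arms: assessor visits at 6 and 12 months = 2 (section 5.2).
- Intervention only: 1 initial visit plus at least 4 = at least 5 (section 7.3).
- Intervention total: at least 2 + 5 = 7. Control total: 2. Ratio of contacts: at least 7/2 = 3.5.
- One reading of the Table 2 example gives about 11 against 2.

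**Step 2. Events that depend on recall (assumed model)**
The documents give no AE rates and no recall data. Assume events occur uniformly in time at the same rate in both arms, and that the chance of reporting an event decays exponentially until the next elicitation, with half-life h months and k = ln 2 / h. The fraction captured over T months, with intervals of length L between elicitations, is

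f = (1/T) × Σ (1 − e^(−kL)) / k.

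Take controls at L = 6, 6 and the intervention arm at 7 evenly spaced contacts (L = 12/7). Example for h = 1, k = 0.693:
- control: 2 × (1 − 2^(−6)) / 0.693 / 12 = 0.237
- intervention: 7 × (1 − 2^(−12/7)) / 0.693 / 12 = 0.585
- ratio: 0.585 / 0.237 = 2.47

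| Half-life (months) | Control, year 1 | Intervention, year 1 | Ratio, year 1 | Ratio, 36 months |
|---|---|---|---|---|
| 1 | 0.237 | 0.585 | 2.47 | 1.59 |
| 3 | 0.541 | 0.826 | 1.53 | 1.20 |
| 6 | 0.721 | 0.907 | 1.26 | 1.09 |
| 12 | 0.845 | 0.952 | 1.13 | 1.04 |
| 120 (hard events) | 0.983 | 0.995 | 1.01 | 1.00 |

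The 36-month column assumes that coordinator contact ends at month 12. Even spacing captures the most for a given number of contacts. With the assessor visits fixed at months 6 and 12 and coordinator visits at an assumed 0.25, 1.5, 3, 4.5 and 9 months, the year-1 ratios for half-lives of 1, 3, 6 and 12 months are 2.25, 1.46, 1.23 and 1.11.

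**Step 3. Suicidal ideation (assumed per-assessment probability)**
Let p be the chance of a positive answer at one assessment, the same in both arms. The documents give no value; 2% to 10% is used for illustration. Assume the PHQ-9 is given at all 7 contacts.
- Independent assessments: P(at least one in n) = 1 − (1 − p)^n.
- Within-person correlation 0.5 (beta-binomial): P = 1 − Π (1 − p/(1 + i)), i = 0 to n − 1.

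| p | Independent: control (n = 2) vs intervention (n = 7) | Ratio | Correlation 0.5: control vs intervention | Ratio |
|---|---|---|---|---|
| 2% | 4.0% vs 13.2% | 3.3 | 3.0% vs 5.1% | 1.7 |
| 5% | 9.8% vs 30.2% | 3.1 | 7.4% vs 12.3% | 1.7 |
| 10% | 19.0% vs 52.2% | 2.7 | 14.5% vs 23.5% | 1.6 |

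At correlation 1 the ratio is 1.

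**Step 4. Common visits only**
Restricted to months 6, 12, 18, 24 and 36, both arms have the same 5 post-baseline elicitation points, and the modelled ratio is 1.0 at every half-life.

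**The case against.** The strongest reply is that the plan specifies no biased comparison. Section 10 has no safety analysis, and the annual summary in section 9.3 is not stated to be by arm. A reader might infer that the plan pools all sources into a by-arm table; the documents do not say so. They are silent on how sources are combined. This part of the reply stands and limits the point to counts that are given to the DSMB or reported by arm.

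A reader might also infer that every by-arm safety table would show an excess, or that the intervention arm would show 3.5 times as many events. Neither is supported. The 3.5 is a ratio of contacts. The assessor asks both arms about AEs and SAEs, hospitalisations and procedures are collected in both arms and utilisation is also taken from charts (section 6, Table 3, section 10.2), and prompt reporting of deaths and unanticipated SAEs runs from the site investigator's knowledge of the event rather than from a visit. Hard events should therefore be nearly equally captured. A true benefit of the intervention could also offset the bias in the observed counts.

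The largest ideation figures (13% to 52% in the intervention arm) need independence between repeated answers from the same person, which is unlikely, and a PHQ-9 at every coordinator visit. Table 4 marks the PHQ-9 for these visits, but section 5.2 describes the interim data more loosely. Candidates at the highest suicide risk are excluded at screening, which makes the assumed probabilities less certain still.

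There are partial safeguards. Coordinator entries are labelled as interim visits in the DS-EHR, so source may be recoverable. Self-harm procedures apply to both arms, each AE is graded for severity and attribution, and the DSMB includes a statistician. None of these sets a rule for the table.

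**Conclusion.** The point holds in limited form. The collection rule itself makes ascertainment unequal: at least 7 against 2 elicitation points in year 1. Nothing in the documents offsets this for events that depend on being asked. The expected direction is towards more recorded events in the intervention arm; the size differs by event type and cannot be derived from the documents.

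Under the stated assumptions, the year-1 ratio with equal true rates is about 1.0 for hard events and up to about 2.5 for events forgotten within a month or so. For ideation it is about 1.7 at a within-person correlation of 0.5 and about 3 under independence. Over 36 months the recall-based ratios shrink to between 1.00 and 1.59 if coordinator contact stops at month 12. Section 5.2 puts the care programme at 12 months, while section 6.2 has coordinators monitoring to 36 months. These passages should be reconciled, because longer contact would prolong the imbalance.

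No pre-specified hypothesis test is affected. This is an inexpensive improvement to safety reporting and does not threaten the trial's main conclusion.

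**What to change.** 1. Add a source field to the AE/SAE form: assessor visit, care-coordinator contact, or other. Capture it prospectively, since it may be hard to reconstruct later.
2. State in section 10 that the primary by-arm safety comparison uses events ascertained at the common blinded assessor visits, plus deaths and hospitalisations from any source.
3. Show the all-source table beside it, with coordinator-detected events identified, so that treatment side effects found by coordinators stay in view. Give the DSMB both tables.
4. Leave participant monitoring and expedited reporting unchanged.

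The cost is one field and one extra table. The common-visit table omits some intervention-arm events. It may also not equalise recall fully, because a participant who has already described an event to a coordinator may remember it better at the assessor visit.
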